**1 SCHEDULE OF STUDY ACTIVITIES**

Study Visit	1	2	3	4	5	6	7
Study Time Point	Day -28 To Day -1	Day 1	Day 14	Day 28	Day 42	Day 56	Month 3
Visit Type (Visit Window)	Screening	Infusion Visits (±1 day)					±7 days
CLINICAL							
Informed consent	X						
Inclusion/Exclusion	X	X					
Medical Hx/Prior/Baseline Medications	X						
NIA criteria review	X						
Modified Hachinski Ischemia Scale	X						
Vital Signs	X	X	X	X	X	X	X
Physical Exam	X	X 					X
Neurological Exam	X	X 					X
ECG	X						
Florbetapir -PET (Appendix C)	X						X
Retinal scan for amyloid (Appendix D)	X						X
Mini Mental State Exam (MMSE)	X						
CDR-SB	X						
IGA deficiency	X						
Serum viscosity	X						
CBC, Chemistry Panel (Appendix B)	X						X
TSH, Vit-B12, RPR 	X						
Urinalysis 	X						
Adverse events & Concomitant Meds		X	X	X	X	X	X
THERAPY							
Infusion of IVIG		X	X	X	X	X	
Assess infusion site		X	X	X	X	X	
 RPR, B12, TSH required if not done in the last 12 months prior to screening							
 Urine culture may be performed if indicated							
 May occur within 72 hours prior to first infusion							

## 2 BACKGROUND

Alzheimer's disease (AD) is a neurodegenerative disorder which causes cognitive decline and brain atrophy associated with the pathologic accumulation of amyloid and tau proteins. Passive immunization with intravenous immunoglobulin (IVIG) contains amyloid antibodies and has been investigated as a potential safe disease-modifying strategy for A $\beta$  clearance in AD.

We conducted the first study investigating early administration of IVIG given in the pre-dementia stage, MCI (mild cognitive impairment), of AD. The details of this randomized, double-, placebo-controlled trial have been previously published. Patients with MCI were randomized to receive either 0.4 g/kg of IVIG or 0.9% saline solution every 14 days x 5 infusions. The results showed that there was less brain atrophy in participants given IVIG when compared with placebo at 12 months as well as evidence of a sustained effect at 36 months based on our extension study results.

We suspect the primary mechanism of action of IVIG to be clearance of amyloid. However other possible mechanisms of IVIG have been proposed. IVIG also contains tau antibodies and has other immunomodulating properties including regulating effects on microglia which may be beneficial in modulating neuroinflammation and neurodegeneration in AD.

There has never been a published study in humans using amyloid imaging to demonstrate the treatment effects of IVIG in MCI. Here we propose use of both amyloid brain PET imaging and retinal amyloid imaging (a novel surrogate scanner used to determine amyloid burden) to determine if IVIG treatment results in a measurable reduction in amyloid.

## 3 STUDY OBJECTIVES AND ENDPOINTS

### 3.1 Primary Objective

This is a proof of concept study is to determine if changes in brain amyloid levels as measured by Florbetapir PET, as well as retinal amyloid levels in the retina are evident three months after infusion of 0.4 g/kg of IVIG every 14 days x 5 infusions.

### 3.2 Primary Endpoints

Change in standard uptake values (SURV) as measured by Florbetapir PET at baseline and 3 months and Retinal Amyloid Index (RAI) as measured by amyloid levels in the retina.

## 4 STUDY PLAN

### 4.1 Study design

This is a single center, open label, proof of concept, out-patient study. Subjects will undergo Florbetapir PET and have retinal amyloid levels measured, receive an infusion of IVIG at 0.4 g/kg every 14 days for a total of five infusions, and repeat PET and retinal amyloid measures three months after the first infusion.

### 4.2 Subject population

The study population will consist of male and female subjects diagnosed with mild cognitive impairment (MCI) due to Alzheimer disease (AD).

### **4.3 Estimated study duration**

The duration of each study subject is approximately 4 months, including one screening visit over a period of approximately 28 days, 5 days of infusions over a 2-month period of time, and a follow-up visit at 3 months after the first infusion.

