## **8 EVALUATIONS BY VISIT**

The overall summary of study activities by visit is provided Section 1.

Screening procedures at visit 1 will take place up to 28 days prior to Visit 2 (Day 1) dosing. Screening labs and assessments will be performed during the screening period. The first dose of study drug is administered on Day 1. Visits 2 through 6 have a  $\pm 1$  day window and occur every 14 days over two months. The investigator will determine if a subject is suitable to continue following a missed infusion. Visit 7 has a  $\pm 7$  day window.

All study screening data from Visit 1 including laboratory results must be reviewed for study eligibility prior to receiving first dose of study drug. Prior to infusion, a review of concomitant medications and AEs takes place. If the subject continues to be eligible for enrollment, the subject will be infused with study medication and will remain in the infusion clinic for at least 1 hour following the infusion for safety assessments on Visit 2 (Day 1), and 15 minutes for the subsequent visits.

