### **8.3 VISIT 3 (Day 14 - Second Infusion) through VISIT 6 (Day 56 - Fifth Infusion)**

- Assess and record AEs
- Record concomitant medications
- Record vital signs
- If there is any abnormality of vital signs or clinical concerns during infusion visit, the principle-investigator or sub-investigator will be paged in order to perform a clinical assessment.
- Preparation of study drug by pharmacists and deliverer to the infusion administration site.
- Administer drug as stated in 8.2.1 and 8.2.2
- Subjects will remain in the clinic for at least 15 minutes following the completion of the infusion. The subjects may leave the clinic after the observation period if the subject is medically stable.

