#### **10.7 Reporting of adverse drug reactions and other safety information**

All suspected AEs and other safety information associated with the administration of Octagam have to be reported to:

Central Drug Safety Unit:

Email:

[[contact]](mailto:[contact])

[contact]

Serious adverse drug reactions have to be reported immediately by fax or email (within 24 hrs). Non-serious adverse drug reactions and other safety information should be reported to Octapharma, if possible, upon recognition but no later than 10 days.

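### After the fifth infusion no contact is scheduled until Visit 7, about 5 weeks later at Month 3, whereas infusions 1 to 4 are each followed by an adverse-event enquiry within about 2 weeks

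*Combined protocol and SAP*

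**What the plan says.** Section 1 and Section 8.3 place the infusions on Days 1, 14, 28, 42 and 56. Section 8 gives Visits 2 through 6 a ±1 "day window and occur every 14 days over two months". It also states: "Prior to infusion, a review of concomitant medications and AEs takes place". Section 8.3 lists AE and concomitant-medication recording at each of Visits 3 to 6, and Section 1 marks that row at Visits 2 to 7 and nowhere else.

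For infusions 2 to 5, Section 8.3 says: "Subjects will remain in the clinic for at least 15 minutes following the completion of the infusion". After the fifth infusion the next column in Section 1 is Visit 7, at Month 3 (±7 days). Section 4.3 agrees ("5 days of infusions over a 2-month period of time, and a follow-up visit at 3 months after the first infusion"), as does Section 4.1 ("repeat PET and retinal amyloid measures three months after the first infusion"). Section 8.4, however, heads Visit 7 as Month 4. No call, visit or blood draw is listed between Day 56 and Visit 7.

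Section 10.1 keeps AE collection open until Visit 7 or the early termination visit, and requires each AE to be assessed for duration, severity, seriousness and relatedness. Section 10.5 requires details of each episode, and covers events that the patient reports as well as those that the investigator observes.

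**The concern.** The repeated infusion visits do a second job that the plan does not name: each is the occasion on which someone asks the subject what happened after the previous infusion. That works for infusions 1 to 4. It stops at the fifth, because no later infusion visit exists. The plan counts the weeks after Day 56 as observed time but schedules no enquiry until they are over.

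Two things are at stake. The first is data quality. Onset, duration and severity would have to be recalled after about 5 weeks, by subjects enrolled because of cognitive impairment. The second is awareness. Section 10.2 names thromboembolic events and suspected transmission of an infectious agent among serious events, and these could be treated away from the study clinic. Section 10.7 says "Serious adverse drug reactions have to be reported immediately by fax or email (within 24 hrs", but prompt reporting is of little use if the site first hears of the event weeks later. With five subjects (Section 15), one missed or misdated event is a visible share of the safety data.

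Concomitant-medication review lapses over the same period. The concomitant-therapy section bars routine vaccination for four weeks after study drug. After the last infusion that period runs to Day 56 + 28 = Day 84, with no check scheduled inside it at the nominal visit times.

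**Working it through.** **Inputs.** Infusion days 1, 14, 28, 42 and 56 (Sections 1 and 8.3). Window ±1 day for Visits 2 to 6 and ±7 days for Visit 7 (Sections 1 and 8). Visit 7 at 3 months after the first infusion (Sections 1, 4.1 and 4.3) or at Month 4 (Section 8.4). The documents do not convert months to days, so Day 84 and Day 91 are taken for Month 3, and Days 112 to about 122 for Month 4, as assumptions.

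**Formula.** Gap = day of the next scheduled visit − day of the infusion. The shortest and longest gaps move both visits to the ends of their windows.

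**Infusions 1 to 4.** 14 − 1 = 13 days; 28 − 14 = 42 − 28 = 56 − 42 = 14 days. With ±1 day at both ends: 13 − 2 = 11 at the shortest and 14 + 2 = 16 at the longest.

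**Infusion 5.**

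| Reading of Visit 7 | Nominal gap | Shortest | Longest | Ratio to 14 days |
|---|---|---|---|---|
| Month 3 = Day 91 | 91 − 56 = 35 | (91 − 7) − (56 + 1) = 27 | (91 + 7) − (56 − 1) = 43 | 35/14 = 2.5 |
| Month 3 = Day 84 | 84 − 56 = 28 | (84 − 7) − (56 + 1) = 20 | (84 + 7) − (56 − 1) = 36 | 28/14 = 2.0 |
| Month 4 = Day 112 | 112 − 56 = 56 (8 weeks) | 48 | 64 | 56/14 = 4.0 |
| Month 4 = about Day 122 | 122 − 56 = 66 (about 9.4 weeks) | 58 | 74 | 66/14 = 4.7 |

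Even the shortest gap in the table (20 days) is longer than the longest gap after any earlier infusion (16 days). The imbalance therefore does not depend on how a month is counted or on which Visit 7 label is meant.

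**What the gap covers.** In Section 1, laboratory tests and physical and neurological examinations after the first infusion occur only at Visit 7. Infusions 1 to 4 have none of their own. The difference between infusion 5 and the others is therefore only in how soon someone asks about AEs and medications.

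**The case against.** The strongest reply is that the plan does not leave the period unobserved. Section 10.5 requires patient-reported events to be recorded, Visit 7 collects AEs and medications, and Visit 7 is the one post-dose visit with blood tests and full examinations. Subjects have an MMSE of 24 to 30 and an informant, the product is FDA approved (Section 7.1), and the background section says the same five-infusion regimen was given in an earlier randomised trial. This is a five-subject imaging study, and the imaging endpoints are untouched. The monitoring committee may also ask for further safety reports (Section 13.3).

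Much of that stands, and it limits the point to scheduled, active enquiry. It does not close the gap. Spontaneous reporting was equally available after infusions 1 to 4, and the plan asks there as well. The informant need only be in touch with the subject about twice a month (Section 5.1, item 12), and Section 8.4 does not say that the informant takes part in Visit 7.

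Three stronger readings are tempting and are not supported:

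- A reader might infer that the gap falls where risk is highest, because the full course has then been given. The documents give no accumulation, half-life or dose-related AE data, so they do not show that risk peaks after infusion 5.
- A reader might infer that AE counts after infusion 5 cannot be compared with those after earlier infusions. No comparison by infusion number is planned; Section 14.1 covers only graphs of individual imaging changes.
- A reader might infer that the reporting deadlines in Section 10.7 would be breached. For non-serious reactions they are tied to recognition, and late awareness breaks no stated rule. It only delays the report.

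**Conclusion.** The point holds as a modest, inexpensive improvement to safety data collection. After the fifth infusion, active AE and medication enquiry comes about 5 weeks later (35 days, with Month 3 taken as Day 91) instead of about 2 weeks later. It comes 4 weeks later if Month 3 is Day 84, and roughly 8 to 9 weeks later if the Month 4 heading in Section 8.4 is meant. The documents do not allow an estimate of how many events would be missed or misdated, so the harm is a risk of late awareness and weaker recall, not a demonstrated loss.

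The conflict over the timing of Visit 7 is a plain inconsistency. Section 4.3 puts total participation at about 4 months including screening, which might explain the Month 4 label, but the text does not say so and Section 1 counts from Day 1.

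**What to change.** Add to Section 1 and Section 8.3 one telephone contact with the subject and the informant about 14 days after the fifth infusion (56 + 14 = about Day 70), covering AEs and concomitant medications with the enquiry used at the infusion visits. This brings the timing of active enquiry after infusion 5 into line with infusions 1 to 4. A call does not replace an in-person review with vital signs, so it aligns timing and not method.

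Reconcile the timing of Visit 7 across Sections 1, 4.1, 4.3 and 8.4. After a Day 70 call, the remaining interval would be 91 − 70 = 21 days, or 84 − 70 = 14 days, under Month 3. Under Month 4 it would be 112 − 70 = 42 to about 122 − 70 = 52 days, and whether one call is enough should then be reconsidered.

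The cost is five short calls by existing staff, one column in the schedule, and possibly a few more recorded AEs. Dosing, imaging and clinic visits stay as they are.

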## **5 SUBJECT SELECTION**

### **5.1 Inclusion criteria**

1. Age 50 to <85 years.
2. Evidence of amyloid pathology on Florbetapir PET at screening.
3. Diagnosis of MCI due to AD based on NIA-AA criteria. (APPENDIX A)
4. MRI brain (with past 24 months) which shows evidence of mild hippocampal atrophy and/or bilateral parietal atrophy.
5. CDR score of 0.5
6. Mini-Mental State Examination (MMSE) score of 24-30, inclusive.
7. Rosen Modified Hachinski Ischemic score  $\leq 4$ .
8. Receiving stable doses of medication(s) for the treatment of non-excluded medical condition(s) for at least 30 days prior to screening. Cholinesterase inhibitors and memantine are allowed if doses have stable been least 30 days prior to screening.
9. Agree to refrain from participating in any treatment or clinical trial targeting amyloid for the duration of the study.
10. Agree to refrain from taking any herbal supplement considered to enhance cognition unless approved by the investigator for the duration of the study.
11. Ability to attend all clinical visits and have an informant capable of accompanying the subject on specific clinic visits.
12. The subject's collaborative informant (support person) must be someone who has known the subject for at least 4 years and has had approximately 2 or more separate communications with the study participant per month (at least one of these communications in person).
13. Fluency in English and evidence of adequate premorbid intellectual functioning.
14. Adequate manual dexterity, visual, and auditory abilities to perform all aspects of the cognitive and functional assessments.
15. Venous access suitable for repeated infusions and phlebotomy.
16. In the opinion of the investigator, the subject and informant will be compliant and have a high probability of completing the study, including all scheduled evaluations and required tests.

### **5.2 Exclusion criteria**

1. Has significant neurological disease other than MCI that in the opinion of the investigator may affect cognition.
2. History of clinically evident stroke or history of clinically significant carotid or vertebrobasilar stenosis or plaque.

3. History of seizures, excluding febrile seizures in childhood.
4. History of screening visit brain MRI scan indicative of any other significant abnormality, including but not limited to multiple microhemorrhages (2 or more), history or evidence of a single prior hemorrhage > 1 cm^3, multiple lacunar infarcts (2 or more) or evidence of a single prior infarct > 1 cm^3, evidence of a cerebral contusion, encephalomalacia, aneurysms, vascular malformations, subdural hematoma, or space occupying lesions of significance as determined by the PI (e.g., arachnoid cysts or brain tumors such as meningioma).
5. Brain MRI shows moderate or severe cortical or hippocampal atrophy.
6. Sensitivity to Florbetapir.
7. Other present/planned ionized radiation that, in combination with planned exposure to PET ligands for this study, would result in cumulative exposure that would exceed recommended limits.
8. Ophthalmologic condition that would interfere with retinal amyloid imaging.
9. Current presence of a clinically significant major psychiatric disorder (e.g., Major Depressive Disorder) according to the criteria of the Diagnostic and Statistical Manual of Mental Disorders, Fourth Edition (DSM-IV-TR) or symptom (e.g., hallucinations) that in the opinion of the investigator could affect the subject's ability to complete the study.
10. Current clinically significant systemic illness that is likely to result in deterioration of the subject's condition or affect the subject's safety during the study including but not limited to renal failure or myocardial infarction.
11. History of cancer within the last 5 years, with the exception of nonmetastatic basal cell carcinoma, and squamous cell carcinoma of the skin.
12. Uncontrolled hypertension (diastolic BP> 100 mmHg or systolic BP> 160 mmHg, sitting).
13. History or evidence of any clinically significant autoimmune disease or disorder of the immune system (e.g., Crohn's Disease, Rheumatoid Arthritis)
14. Clinically significant infection within the last 30 days (e.g., chronic persistent or acute infection (eg, upper respiratory infection [URI], urinary tract infection [UTI]).
15. Female subjects of childbearing potential.
16. Other clinically significant abnormality on physical, neurological, laboratory, vital signs or ECG examination (e.g., atrial fibrillation) that could compromise the study or be detrimental to the subject.
17. Weight greater than 120 kg (264 lbs).
18. Excessive smoking defined as more than 20 cigarettes per day.

19. History of alcohol or drug dependence or abuse as defined by DSM-IV criteria within the last 2 years.
20. Severe liver or kidney disease verified by the PI review of ALT, AST and creatinine.
21. Known coagulopathy, thrombosis, or low platelet count.
22. Hemoglobin less than 11 g/dL.
23. Known deficiency to IgA.
24. Positive serology for Hepatitis B or C, or HIV.
25. History of anti-amyloid treatment, immunotherapy, or other experimental treatment for MCI or Alzheimer disease.
26. Concurrent use of anticholinergic drugs including diphenhydramine.
27. Current use of anticoagulant medications (except the use of aspirin 325 mg/day or less, plavix, aggrenox, and persantine but not for stroke).
28. Concurrent use of opioid pain relievers and related synthetic derivatives.

## **6 ENROLLMENT**

Prior to the start of enrollment, all study contracts must be fully executed and the following critical documents must be filed in the sponsor's regulatory binder (trial master file):

- Investigational new drug (IND) application approved by the FDA
- Sutter Health Institutional Review Board (SHIRB) approval of the study protocol and the informed consent form (ICF)
- Signed and dated study protocol
- Completed Federal Drug Administration (FDA) Form 1572
- Current curricula vitae and medical licenses (if applicable) of the Principal Investigator (PI) and all Sub-Investigators listed on the Form FDA 1572;
- Name, address, and membership of the IRB, and/or written statement that IRB is properly constituted and operates according to Good Clinical Practices (GCP)
- Investigator's Brochure
- Laboratory normal range and documentation of laboratory certification (or equivalent).
- All applicable contracts

### **6.1 Enrollment**

A subject is considered enrolled when they have completed informed consent and received any amount of IVIG by infusion.

## **7 STUDY DRUG AND TREATMENT**

### **7.1 Description of study drug**

Octagam is an FDA approved 10% human normal immunoglobulin solution ready for intravenous administration. Adverse Drug Reactions (ADRs) reported for Octagam are expected to be similar in type and intensity to those reported with other IVIG preparations.

The Octagam manufacturing process achieves a significant viral reduction through a combination of two dedicated manufacturing process steps: solvent/detergent (S/D) treatment and nanofiltration (20 nm). Based on the combination of these two steps, Octagam complies with the latest international consensus on best practices for viral safety. The Source Q chromatography (ion-exchange chromatography) step in the Octagam process also contributes significantly to the viral safety of Octagam. The efficacy of the virus inactivation procedures has been extensively validated according to relevant international guidelines in place. Further information can be found in the current Investigator's Brochure.

### **7.2 Shipping, handling, and storage**

Octagam will be shipped directly to the pharmacy or investigational site, after all required regulatory and legal documents have been received by the Sponsor.

Upon receipt of the study drug shipments, the pharmacist will verify the condition of the study drug and perform study drug accountability. Acknowledgement of receipt will be documented in the Pharmacy Binder. A temperature logger showing the transport temperature will be read out by the shipper and release the drug if the transport temperature is verified to be between +2°C to + 8°C (36°F to 46°F). If there was a deviation from this temperature range, an Octapharma Project Manager or Qualified Person must assess the temperature log and approve release.

The study drug will be stored in a secure area with access restricted only to authorized personnel. Octagam may be stored for 15 months at +2°C to + 8°C (36°F to 46°F) from the date of manufacture.

### **7.3 Special precautions for storage**

- Do not freeze. Frozen product should not be used
- Do not use after expiration date

### **7.4 Drug accountability**

The investigator is responsible to ensure supervision of accurate monitoring of the receipt, storage and allocation of the study drug. Copies of all invoices of study drug shipments must be retained. Accurate study drug inventory, dispensing and accountability logs must be obtained and stored in the Pharmacy Binder.

### **7.5 Study drug dosage**

The dose level of IVIG at 0.4 g/kg will be administered by IV infusion once every 14 days for two months. Subject's weight at the first infusion visit will be used for the dosing calculation for the remaining infusions. There is no provision for dose adjustments by the investigator under this protocol.

